7.1.2 Temporary discontinuation

Temporary intervention discontinuation, because of suspected AEs or disruption of the clinical trial due to a regional or national emergency declared by a governmental agency (Appendix 10 [Section 10.10]: Contingency measures for a regional or national emergency that is declared by a governmental agency) may be considered by the Treating Investigator. For all temporary intervention discontinuations, duration should be recorded by the Investigator in the appropriate pages of the eCRF.

If surgery is needed during the study, the benefit-risk of withholding the IMP for at least 3 to 7 days pre- and post-surgery and the risk of bleeding should be considered.

The following shall lead to temporary treatment discontinuation:

- Cytopenias: algorithm for neutropenia and thrombocytopenia as per Appendix 6 (Section 10.6) should be followed.
- Serum creatinine, creatine phosphokinase (CPK) and liver enzyme increase: follow corresponding algorithms as per Appendix 6 (Section 10.6).
- Cardiac arrhythmia (Atrial fibrillation): Any Grade 3 event (symptomatic, urgent intervention indicated; device [eg, pacemaker]; ablation; new onset).
- Suicidal risk as per C-SSRS: if a participant scores "yes" on items 4 or 5 of the Suicidal Ideation Section, or "yes" on any item of the Suicidal Behavior Section.

If needed, temporary treatment discontinuation can be considered by the Investigator or by the participant for any other reason, including due to any safety concerns because of disruption of the clinical trial due to a regional or national emergency declared by a governmental agency such as COVID-19 (Appendix 10 [Section 10.10]) or another illness or if there is a need for a prohibited concomitant medication. Treatment can be resumed later when it is considered safe and appropriate.

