 - Call the participant immediately to reschedule the next LFTs timepoint as soon as possible and discuss with them about the underlying reasons of missing the timepoints.
 - Instruct participant to hold IMP immediately if they decline to reschedule the timepoint or miss the rescheduled timepoint.
 - Inform the participant that IMP can resume only after LFTs monitoring compliance is achieved.
 - Inform the monitoring team of any underlying reason identified for participant noncompliance and work with the monitoring team to resolve underlying issues to ensure compliance.

Amended Clinical Trial Protocol 12 SAR442168-EFC16645 - tolebrutinib 20-Dec-2023 Version number: 1

*If unable to retest in 72 hours, use original laboratory results to decide on further reporting/monitoring/discontinuation.

[figure not shown]
Note: "Baseline" refers to ALT sampled at baseline visit; or if baseline value unavailable, to the latest ALT sampled before the baseline visit. The algorithm does not apply to the instances of increase in ALT during screening. See Section 8.3 for guidance on safety reporting. Normalization is defined as \leq ULN or baseline value if baseline value is > ULN.

In ANY CONFIRMED CASE of ALT >5 x ULN or ALT >3 x ULN with bilirubin >2 x ULN, the following steps are REQUIRED (recommended for ALT >3 x ULN but ALT <5 x ULN, as clinically indicated):

- INFORM the Site Monitor, who will forward the information to the Study Manager.
- INVESTIGATE specifically for malaise with or without loss of consciousness, dizziness, and/or hypotension and/or episode of arrhythmia since the last visit, particularly in the previous 72 hours; rule out muscular injury.
- **PERFORM** the following tests/actions:
 - LFTs: AST, ALT, alkaline phosphatase, GGT, total and conjugated bilirubin, and prothrombin time/INR (mandatory assessments for ALT >3 x ULN);
 - CPK, serum creatinine, complete blood count;
 - Anti-HAV IgM, anti-HBc IgM, (HBV-DNA if clinically indicated), hepatitis B surface antigen (HBsAg), anti-HCV and HCV RNA, anti-CMV IgM and anti-HEV IgM antibodies;
 - Iron, ferritin, transferrin saturation;
 - Auto-antibodies: serum IgG levels, antinuclear, anti-DNA, anti-smooth muscle, anti-LKM, anti-mitochondrial;
 - Evaluate recent infection with EBV, herpes viruses. Depending on the clinical context, consider testing for toxoplasma:
 - Collect and freeze serum sample (5 mL x 2);

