 - Collect and store one PK sample following the instructions in the central laboratory manual;
 - Perform-hepatobiliary imaging (ultrasonography or other imaging investigations is required);
 - Consider DNA test for Gilbert's disease if clinically indicated;
 - Recommend consulting a hepatologist (mandatory if ALT >8 x ULN or is associated with elevated bilirubin);
 - Discuss with the hepatologist the clinical indication for potential liver biopsy (strongly recommended if the participant meets Hy's law criteria or has ALT >20 x ULN) and/or initiation of treatment with steroids;
 - Consider patient hospitalization if INR >2 (or PT <50%) and/or central nervous system disturbances suggesting hepatic encephalopathy.
- MONITOR LFTs after discontinuation of IMP:
 - Monitor closely (every 2-3 days) until ALT is down-trending, then weekly until <1.5 x ULN, and then at every scheduled visit;
 - This frequent LFT monitoring may be done through central or local lab, or via home visit (depending on the Investigator's assessment and/or local regulatory requirements).
- RECHALLENGE: Re-initiation of the study drug can only be considered after discussion with the Sponsor's Medical Monitor once the ALT/AST decreases to <1.5 x ULN, and there is no clinical contraindication. Rechallenge is not permitted for the following participants unless a clear non-DILI etiology is identified:
 - ALT >8 x ULN
 - ALT >5 x ULN for greater than two weeks
 - ALT >3 x ULN and total bilirubin >1 x ULN
 - In case it is agreed to re-start the study drug, it is recommended that ALT/AST be assessed per protocol schedule of assessments for the first 6 months of the treatment period.
 - The occurrence of new elevation to >3 x ULN for the ALT/AST values will lead to permanent discontinuation of the study drug.

ALT, alanine aminotransferase; AST, aspartate aminotransferase; CMV, cytomegalovirus; CPK, creatine phosphokinase; CRF, case report form; EBV, Epstein-Barr virus; GGT, gamma glutamyl transferase; HAV, hepatitis A virus; HBV, hepatitis B virus; HCV, hepatitis C virus; HEV, hepatitis E virus; IgG, immunoglobulin G; IgM, immunoglobulin M; IMP, investigational medicinal product; INR, international normalized ratio; LFT, liver function test; LKM, liver-kidney microsomal antibody; PT, prothrombin time; ULN, upper limit of normal.

[figure not shown]
INCREASE IN SERUM CREATININE in patients with normal baseline (creatininemia between 45 µmol/L and 84 µmol/L)

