#### Analyses according to PCSA

Potentially clinically significant abnormality (PCSA) analyses will be performed based on the PCSA list currently in effect at Sanofi at the time of the database lock. For parameters for which no PCSA criteria are defined, similar analyses will be done using the normal range.

Analyses according to PCSA (normal range) will be performed based on the worst value during the DB treatment-emergent period and OL period, using all measurements (either local or central, either scheduled, nonscheduled or repeated).

For laboratory variables, vital signs, and ECG variables above, the incidence of participants with at least one PCSA during the DB treatment-emergent period and OL period will be summarized respectively regardless of the baseline level and according to the following baseline status categories:

- Normal/missing
- Abnormal according to PCSA (normal range) criterion or criteria

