#### Additional analyses for drug-induced liver injury

The following additional analyses will be performed for drug-induced liver injury:

- Time to onset of the initial ALT or AST elevation (>3 x ULN) and total bilirubin elevation (>2 x ULN) during the treatment-emergent period will be analyzed using the KM method.
- The KM method will also be used to analyze time to onset of the following initial elevation ALT >3 x ULN, ALT >5 x ULN, ALT >8 x ULN, ALT >10 x ULN, AST >3 x ULN, AST >5 x ULN, AST >8 x ULN, AST >10 x ULN, total bilirubin >2 x ULN during the treatment-emergent period, respectively.
- A graph of the distribution of peak values of ALT versus peak values of total bilirubin during the treatment-emergent period will be provided.
- For each liver function test (eg, ALT), participants having experienced a PCSA (eg, ALT >5 x ULN) will be summarized using the following categories: Returned to baseline PCSA status (or returned to value ≤ULN in case of missing baseline) before last IMP dose, Returned to baseline PCSA status after last IMP dose, Never returned to baseline PCSA status, No assessment after elevation. This summary will be performed by categories of elevation ALT >3, >5, >10, >20 x ULN.

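### The SAP's liver-recovery table pools recovery on drug with recovery during an interruption that ended in a restart, and it does not show normalization

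*SAP*

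**What the plan says.** SAP section 3.6.3.1, under the additional analyses for drug-induced liver injury, specifies one recovery table. On who enters it: "participants having experienced a PCSA (eg, ALT >5 x ULN) will be summarized using the following categories". The first category is "Returned to baseline PCSA status (or returned to value ≤ULN in case of missing baseline) before last IMP dose" and the others are "Returned to baseline PCSA status after last IMP dose, Never returned to baseline PCSA status, No assessment after elevation". On strata: "This summary will be performed by categories of elevation ALT >3, >5, >10, >20 x ULN". The preceding SAP text on PCSA analyses gives baseline status two levels, normal or missing on one side and "Abnormal according to PCSA (normal range) criterion or criteria" on the other.

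Protocol section 7.1.2 lists a liver enzyme increase among the events leading to temporary discontinuation, following the Appendix 6 algorithm. Protocol section 10.6 (Appendix 6) allows re-initiation to be considered only "once the ALT/AST decreases to <1.5 x ULN, and there is no clinical contraindication". A note to the ALT algorithm in the same appendix defines normalization as at or below "ULN or baseline value if baseline value is > ULN". On data collection, section 7.1.2 states: "For all temporary intervention discontinuations, duration should be recorded by the Investigator in the appropriate pages of the eCRF". Protocol section 6.5 also has intervention start, stop and delay dates entered in the eCRF.

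**The concern.** The protocol names drug-induced liver injury, including severe cases, as an identified risk (section 2.3). For an elevated ALT, a safety reader wants to know whether the value settled while the drug continued, settled because the drug was withheld, or came back when it was restarted. The table uses one time anchor, the last IMP dose, and makes no allowance for gaps in dosing before it. The SAP's exposure duration (section 3.6.1) likewise runs from first to last dose and ignores gaps.

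The second difficulty is the yardstick. Return to baseline PCSA status is a change of category, not a return to normal or to the participant's own baseline value. At stake is how the recovery rows can be read: how much recovery happened on continued drug, and how much of it was complete. Hypothesis tests, type I error and power are not affected.

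**Working it through.** The plan states no figure on this point, so there is none to reproduce. The check applies the four categories literally.

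**Inputs**
- Return criterion, four rows and strata: SAP 3.6.3.1.
- Restart condition, ALT/AST below 1.5 x ULN: protocol 10.6.
- Rechallenge barred for ALT >8 x ULN, ALT >5 x ULN for more than two weeks, or ALT >3 x ULN with total bilirubin >1 x ULN, unless a clear cause other than drug injury is found: protocol 10.6.
- Confirmed screening ALT >1.5 x ULN excluded, with limited exceptions: protocol 5.2, E 05.
- ALT PCSA cut-off: not in the documents. Assumed range >3 to >5 x ULN, from the SAP's own example and lowest stratum.

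**Step 1: the time anchor.** The restart limit of 1.5 x ULN lies below both 3 and 5 x ULN. Anyone held for an ALT above the PCSA cut-off, with a non-PCSA baseline, and restarted under Appendix 6 has therefore already met the return criterion off drug. A restart means a later last dose. Recovery is then dated before the last dose.

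**Step 2: illustrative courses.** These are invented, with ALT in multiples of ULN. I assume that the first return counts, since the SAP does not say which episode counts after a second rise. I also assume that the missing-baseline clause applies to every row, although the SAP prints it only in the first.

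| Course | Baseline | ALT and dosing | Last dose | Row, PCSA >3 | Row, PCSA >5 |
|---|---|---|---|---|---|
| A | 0.8 | 6, 4, 0.9; dosing throughout | Day 900 | Before | Before |
| B | 0.8 | 6; held day 43; 4, 1.2 off drug; restart day 70 | Day 900 | Before | Before |
| C | 0.8 | as B, then 3.5 on day 84; permanent stop | Day 85 | Before | Before |
| D | 0.8 | 6; permanent stop; 4, 0.9 | Day 43 | After | After |
| E | 0.8 | 6, 2.9, 2.5; dosing throughout | Day 900 | Before | Before |
| F | Missing | as E | Day 900 | Never returned | Never returned |
| G | 0.8 | 22; permanent stop; 9, 4.8 | Day 43 | Never returned | After |

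A (recovery on drug), B (recovery off drug, then restart), C (recurrence after restart) and E (never at or below ULN) share one row at either cut-off. D is placed correctly.

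**Step 3: what the rows can bear.** By the table's own return criterion:
- before-last-dose row = recovered while taking IMP + recovered during an interruption, then restarted
- all off-drug recovery = after-last-dose row + recovered during an interruption, then restarted

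The first row is thus an upper bound on on-drug recovery, and the second a lower bound on off-drug recovery. Both are off by the same unknown count.

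**Step 4: where it bites.** Since 10 and 20 exceed 8, the rechallenge bar keeps most participants in the >10 and >20 x ULN strata from restarting. The mixing sits mainly in the >3 and >5 strata. Protocol 10.8.3 (France and Japan) interrupts for every ALT above 5 x ULN. Section 10.8.4 (Japan) adds ALT >3 x ULN with raised INR or bilirubin, though the bilirubin route largely meets the rechallenge bar.

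**Step 5: the yardstick.** With screening ALT limited to 1.5 x ULN, almost every baseline is non-PCSA, so return means only that the criterion is no longer met. Course E counts as returned at 2.9 x ULN. Under the protocol's definition, with a baseline of 0.8, it would have to reach 1.0 or below.

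**The case against.** The row label says only that recovery preceded the last dose. It makes no claim about being on drug or about adaptation, so the restarted participant is placed correctly under the words as written. That is fair, and the point is what the row can support rather than a coding error.

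The protocol's normalization definition is a note to a management algorithm, not an analysis rule, so the documents do not contradict each other. This also stands, but the table still leaves normalization unreported for participants with a baseline value.

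The PCSA list is the one in force at database lock and cannot be seen. The >5 x ULN figure is only an example, and it fits poorly with a >3 stratum that would then add nobody. The SAP also does not say whether return is judged against the stratum or a single cut-off. The finding holds for ALT at either cut-off, but no exact value can be given. The ALT flowchart is not shown, so the frequency of interruption outside France and Japan is unknown.

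The stricter rule for a missing baseline should rarely matter. Biochemistry is scheduled at screening and before the first dose on Day 1, and baseline is the last pre-dose value.

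A reader might infer that the whole liver profile will look better than it is. The documents do not support that. The Kaplan-Meier analyses of time to elevation, the peak ALT against bilirubin plot, the maximum-value plots in SAP 5.5 and the discontinuation summaries do not use this recovery definition. Independent hepatologists review all potential cases (protocol 10.1.5.5), and SAP 5.5 plans a detailed summary for each AESI. Neither of these last two specifies a tabulation by dosing status or of normalization, so the gap in this table remains.

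**Conclusion.** The point holds in limited form. The first recovery row mixes recovery while dosing with recovery during an interruption followed by restart, including restarts after which ALT rose again if the first return is the one counted. For nearly all participants, the table does not show normalization as the protocol defines it.

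The size is one unknown count: participants interrupted, recovered and restarted. The conclusion rests on the literal categories, an ALT PCSA cut-off no lower than the 1.5 x ULN restart limit, and restarts that follow Appendix 6.

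Two stronger readings do not hold. One is that the table cannot tell on-drug from off-drug recovery at all; recovery after a permanent stop is separated correctly. The other is that recovery is credited some number of weeks too early. That needs a rate of ALT decline the documents do not give, and the table has no time axis. The earlier date changes a cell only if ALT plateaus, or the last dose or last sample falls, between the PCSA cut-off and normalization.

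This is a descriptive table, but it is the only recovery tabulation specified for the identified risk, so it should be corrected.

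**What to change.** Keep the existing PCSA rows and make these changes in SAP 3.6.3.1:
- Split the before-last-dose row by dosing status on the recovery date: taking IMP, or during an interruption. For the second group, show how many had a recurrence after restart.
- Add a row for normalization by the protocol's definition, applied to all participants. Where baseline is missing, use at or below ULN.
- State the cut-off against which return is judged, and which episode counts when ALT rises again.

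The intervention start, stop and interruption data are already collected in the eCRF (protocol 6.5 and 7.1.2). The cost is SAP wording and a little more programming. Fewer participants will be shown as recovered on treatment. No clinical rule changes.

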#### 3.6.3.2 Analysis of suicidality assessment

The number (%) of participants with suicidal ideation, suicidal behavior, and self-injurious behavior without suicidal intent based on the Columbia Suicide Severity Rating Scale (C-SSRS) during DB treatment period and OL period will be summarized respectively. A shift table for baseline versus during treatment and OL responses will be provided respectively according to the categories of no suicidal ideation or behavior, suicidal ideation, and suicidal behavior.

#### 3.7 OTHER ANALYSES

#### 3.7.1 Other variables and/or parameters

#### 3.7.1.1 PK analyses

Tolebrutinib and M2 metabolite pharmacokinetic (PK) individual parameters (at least Cmax, tmax, AUC0-24) and corresponding descriptive statistics (mean, geometric mean, median, SD, coefficient of variation, minimum, and maximum) will be determined by population PK analysis by the PKDM department using sampling times at Months 6, 9, and 12.

Tolebrutinib and M2 metabolite PK parameters will be reported in a standalone report outside of the CSR.

#### 3.7.2 Pharmacodynamic (PD) analyses

Blood samples for lymphocyte phenotyping will be collected for a subset of up to 200 randomized participants. Flow cytometry will be used for evaluation of change (and % change) from baseline in lymphocyte count and phenotyping subset. Additional pharmacodynamics evaluations include assessment of neurofilament light chain (NfL) levels in plasma, chitinase-3-like protein 1 (Chi3L1), and immunoglobulin (Ig) levels in serum.

These parameters will be summarized by actual treatment group on the safety population using the following descriptive statistics: mean, geometric mean, median, SD, coefficient of variation, minimum, and maximum.

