#### Table 1 - Objectives and endpoints

	Objectives	Endpoints		
Secor	ndary			
•	To evaluate efficacy of tolebrutinib compared to placebo on clinical endpoints, MRI lesions, cognitive	• Time to onset of sustained 20% increase in the 9-HPT for at least 3 months		
	performance, physical function, and quality of life	
 
Time to onset of sustained 20% increase in the T25-FW for at least 3 months
 
		
		
 
Time to onset of 3-month CDP as assessed by the EDSS score
 
		
		
 
Total number of new and/or enlarging T2-hyperintense lesions as detected by MRI, defined as the sum of the individual number of new and/or enlarging T2 lesions at all scheduled visits starting after baseline up to and including the EOS visit
 
		
		
 
Time to onset of CDI defined as a ≥1.0 point decrease on the EDSS score from baseline confirmed over at least 6 months
 
		
		
 
Percent change in brain volume loss (BVL) as detected by MRI scans at the EOS compared to Month 6
 
		
		
 
Change in cognitive function at the EOS compared to baseline as assessed by SDMT
 
		
		
 
Change in cognitive function at the EOS compared to baseline as assessed by CVLT-II, where available
 
		
		
 
Change in MSQoL-54 questionnaire score from baseline through the EOS
 
		
•	To evaluate safety and tolerability of tolebrutinib	
 
Adverse events (AEs), serious AEs, AEs leading to permanent study intervention discontinuation, AEs of special interest, and potentially clinically significant abnormalities in laboratory tests, safety scales, ECG, and vital signs during the study period
 
		
•	To evaluate population pharmacokinetics of tolebrutinib and relevant metabolite(s) in NRSPMS and its relationship to efficacy and safety	
 
Plasma concentration of tolebrutinib and relevant metabolite(s) (population PK assessment) at Months 6, 9, and 12
 
		
•	To evaluate pharmacodynamics (PD) of tolebrutinib	
 
Change in plasma NfL levels at the EOS compared to baseline
 
		
		
 
Change in lymphocyte phenotype subsets in whole blood at the EOS compared to baseline in a subset of participants
 
		
		
 
Change in serum immunoglobulin level at baseline compared to the EOS
 
		
		
 
Change in serum Chi3L1 levels at baseline compared to the EOS
 
		

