#### 1.2.1 Estimands

The primary estimand for the primary endpoint is summarized in Table 2. More details are provided in Section 3.

In all analyses, the comparison of interest will be the comparison of tolebrutinib versus placebo.

Statistical Analysis Plan SAR442168-EFC16645 - tolebrutinib 30-Apr-2024 Version number: 3

Endpoint	Estimands			
Category (estimand)	Endpoint	Population	Intercurrent event(s) handling strategy	Population-level summary (Analysis and missing data handling)
Primary objective: To	evaluate the efficacy of tole	ebrutinib compared to	placebo in delaying disability progression in NRSPMS	
Primary endpoint (treatment policy estimand)	Time from randomization to onset of 6-month CDP	ITT	Regardless of completion of the treatment period (treatment policy)	Treatment effect on time to onset of 6-month CDP, as measured by the hazard ratio for tolebrutinib compared to placebo, analyzed by a Cox proportional hazards model with terms for treatment group, age at screening (>40, ≤40 years), geographical region (US, non-US), baseline EDSS score and baseline Gd-enhancing T1 lesions (present, absent). The comparison of treatment groups will also be assessed using the log-rank test stratified by age at screening (>40, ≤40 years) and geographical region (US, non- US). Incomplete data will be imputed only for participants who complete the study, meet 3-month CDP criteria, and continue to meet criteria for EDSS disability progression through the final study assessment, but do not reach 6-month confirmation. For other participants without a confirmed 6-month CDP or with premature study discontinuation prior to 6-month confirmation after onset of an event, the participants will be censored at the date of last EDSS

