## **3 STATISTICAL ANALYSES**

#### 3.1 GENERAL CONSIDERATIONS

The baseline values of efficacy parameters are generally defined as the last available value prior to the first dose of study medication unless otherwise specified. In most cases the assessment should be prior to the randomization call, but it is possible that some assessments are performed between the actual randomization call and the first intake of investigational medicinal product (IMP). For the Expanded Disability Status Scale (EDSS) score, the baseline value will be taken as the average of the screening and randomization visit values. If one of the values is missing, the non-missing value will be used as baseline. The baseline value of safety parameters is defined as the last available value prior to the first dose of IMP. For the C-SSRS, the baseline value will be the worst assessment between the past 6 months evaluation at screening and the C-SSRS since last visit evaluation on Day 1. For participants randomized but not treated, the baseline value is defined as the last available value before randomization. Unless otherwise indicated, 2-sided p-values and 95% confidence intervals (CIs) will be provided for treatment comparisons.

To include all participants in analyses where baseline Gd-enhancing T1-hyperintense lesion presence or absence is used as a covariate, baseline status (present or absent) will be imputed for participants with a missing baseline count: if subsequent post-baseline counts for a participant are all 0, then impute baseline status as absent, otherwise, impute baseline status randomly with seed = 16645 based on the proportion of presence/absence at baseline in the overall population. Of note, the number of participants affected is minimal with no impact on results.

In general, continuous data will be summarized using the number of observations available, mean, standard deviation (SD), median, interquartile range (Q1, Q3), minimum, and maximum. Categorical and ordinal data will be summarized using the count and percentage of participants. Efficacy data will be analyzed in the ITT population, and safety data will be analyzed in the safety population, unless specified otherwise.

Unless otherwise specified, analyses will be performed by treatment group and overall for baseline and demographics characteristics.

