#### 3.3 SECONDARY ENDPOINT(S) ANALYSIS

The secondary endpoints detailed in this section are for assessing efficacy of tolebrutinib compared to placebo. Other secondary endpoints analyses are defined in Section 3.6.2 (AE, SAE), Section 3.6.3.1 (laboratory abnormalities), Section 3.7.1.1 (PK) and Section 3.7.2 (PD).

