#### 3.4.2 Main analytical approach

Summary statistics including mean, SD, median, interquartile range (Q1, Q3), minimum, and maximum will be provided for the following continuous data endpoints at scheduled visits over the study period including the EOS. Only non-missing data will be included. For change from baseline, only participants with baseline and post-baseline data will be summarized.

- EDSS score and change from baseline
- Number of Gd-enhancing T1 lesions and change from baseline
- Number of new Gd-enhancing T1 lesions
- Number of new/enlarging T2 lesions per 6-month interval
- T2 lesion volume and change from baseline
- Cumulative number of new T1-hypointense lesions
- T1-hypointense lesion volume and change from baseline.
- Number of phase rim lesions and change from baseline
- Normalized brain volume at screening and percent change in brain volume at post baseline time points
- Number of slowly evolving lesions at EOS compared to screening
- Volume of slowly evolving lesions at EOS compared to screening
- SDMT number of correct substitutions Z-score and change from baseline
- SDMT number of completed items and change from baseline
- CVLT-II standardized scores for total number correct and change from baseline
- CVLT-II standardized scores for total number of intrusions and change from baseline

- CVLT-II standardized scores for total number of repetitions and change from baseline
- MSFC-3 score and change from baseline
- T25-FW raw score and Z-score for leg function/ambulation and change from baseline
- 9-HPT raw score and Z-score for arm/hand function and change from baseline
- MSQoL-54 score and change from baseline for the 2 derived composite scores, 12 subscale scores and 2 single item scores
- EQ-5D-5L health state utility value score and change from baseline
- EQ VAS score and change from baseline

Plots of mean ( $\pm$ SD) and/or mean change ( $\pm$ SD) and/or median over time will also be provided for better visualization.

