#### Other endpoints

Data for magnetization transfer ratio (MTR) recovery at EOS in new MTR lesions detected at Months 6 and 12 and normalized T1 intensity in SELs will be listed.

Actigraphy sub-study data will be collected and processed by an external vendor, Koneksa. Analysis and reporting of this sub-study will be performed separately from the CSR.

Missing data will not be imputed in the analysis of tertiary endpoints, nor will sensitivity or subgroup analyses be conducted.

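### The PD secondary endpoints and the slowly evolving and phase rim lesion endpoints get only unadjusted per-arm summaries; nominal estimates by randomised arm would be a cheap improvement

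*SAP*

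**What the plan says.** SAP Table 1 lists four PD measures as secondary endpoints under the objective "To evaluate pharmacodynamics (PD) of tolebrutinib". One of them is "Change in plasma NfL levels at the EOS compared to baseline"; the others concern lymphocyte subsets, immunoglobulins and Chi3L1. SAP 3.3 sends PD to section 3.7.2, which says: "These parameters will be summarized by actual treatment group on the safety population using the following descriptive statistics". The statistics are mean, geometric mean, median, SD, coefficient of variation, minimum and maximum.

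The chronic-lesion MRI measures are tertiary endpoints. In SAP 3.4.2, phase rim lesions and SEL number and volume appear only in the summary-statistics list, for example "Number of slowly evolving lesions at EOS compared to screening". MTR recovery is listed only, and likewise "normalized T1 intensity in SELs will be listed".

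Two general statements bear on this. SAP 1.2.1 says: "In all analyses, the comparison of interest will be the comparison of tolebrutinib versus placebo". SAP 3.1 says: "Unless otherwise indicated, 2-sided p-values and 95% confidence intervals (CIs) will be provided for treatment comparisons". Protocol 9.4.4 and 9.4.6 leave the methods for tertiary and PD endpoints to the SAP, so the protocol supplies no contrast either.

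**The concern.** Both arms are sampled and scanned, but for these endpoints the plan stops at a column of summaries per arm. A statement about the drug's effect on NfL or SELs would rest on comparing two unadjusted columns, with no prespecified estimate, no confidence interval and no adjustment for baseline.

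For PD, the columns are not clearly the randomised groups. SAP section 2 assigns anyone who receives more than one study intervention to tolebrutinib 60 mg in as-treated analyses. Protocol 6.6.1 lets a participant with 6-month CDP switch to open-label tolebrutinib. Taken literally, a placebo participant who switches would be counted under tolebrutinib, including for samples drawn before the switch. Section 3.7.2 does not say whether that is intended or how samples after the switch are handled.

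The measures matter to the programme. Protocol 2.2 ties progression to smouldering inflammation and names SELs and paramagnetic rim lesions among its imaging features. Protocol 2.3 lists modulation of those lesions as a potential benefit.

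**Working it through.** **1. The plan's own design figure.** The SAP gives no precision or power figure for these endpoints. Its only design figure is 80% power for the primary endpoint with about 288 events, hazard ratio 0.70 and 2:1 allocation (SAP section 4). By the Schoenfeld formula, power = Φ(√(288 × 2/3 × 1/3) × |ln 0.70| − 1.96) = Φ(8 × 0.357 − 1.96) = 81.4%, so the figure reproduces. The point does not depend on it.

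**2. Endpoint by endpoint.** Each measure was looked for in every SAP analysis section.

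| Endpoint | Planned analysis | Between-arm estimate with CI |
|---|---|---|
| NfL, Chi3L1, Ig, lymphocyte subsets (secondary) | Per-arm descriptives, actual treatment, safety population (3.7.2) | None (0 of 4) |
| Phase rim lesions, SEL number, SEL volume (tertiary) | Summary statistics (3.4.2) | None (0 of 3) |
| MTR recovery, T1 intensity in SELs (tertiary) | Listing (3.4.2) | None (0 of 2) |
| T2 lesion volume, MSFC-3, EQ-5D-5L (tertiary) | MMRM (3.4.2) | Yes |
| New Gd-enhancing lesions (tertiary) | Negative binomial (3.4.2) | Yes |
| Brain volume (secondary) | MMRM (3.3.1.2.3), in the hierarchy (3.5) | Yes |

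T1-hypointense lesion measures are also descriptive only.

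**3. What a contrast would deliver, in SD units.** With 2:1 allocation, SE = SD × √(3/N + 1.5/N) = SD × √(4.5/N). Assuming complete data:

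| N | SE (SD) | 95% CI half-width (SD) | Detectable at 80% power (SD) |
|---|---|---|---|
| 1,290 | 0.059 | 0.12 | 0.165 |
| 1,100 | 0.064 | 0.125 | 0.18 |
| 200 (lymphocyte subset) | 0.150 | 0.29 | 0.42 |

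**4. On the NfL scale.** Assumptions not in the documents: SD of log change 0.45 (range 0.3 to 0.6), and 50 to 70% of 1,100 participants with paired values, that is N = 550 to 770.

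- N = 550: SE = 0.45 × √(4.5/550) = 0.0407; half-width exp(1.96 × 0.0407) − 1 = 8.3%.
- N = 770: SE = 0.45 × √(4.5/770) = 0.0344; half-width 7.0%.
- Across SD 0.3 to 0.6 the half-width runs from 4.6% to 11.2%.
- Power for a ratio of 0.90 is Φ(0.105/SE − 1.96) = 73.5% and 86.5% at SD 0.45. Over the full range of assumptions it is 49% to 99.6%, so the power figure settles little; the CI width is the more useful guide.

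**The case against.** The strongest case is that descriptive analysis was a legitimate choice.

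- **No promise is broken.** A reader might infer that SAP 1.2.1, with its reference to all analyses, contradicts section 3.7.2. It does not. That sentence sits under Estimands and names which arms are compared. SAP 3.1 gives p-values and CIs only where a treatment comparison is made, and unless otherwise indicated. SAP 3.3 adds: "The secondary endpoints detailed in this section are for assessing efficacy of tolebrutinib compared to placebo", and sends PD elsewhere. The PD objective names no comparator, and safety is also openly descriptive. This stands.
- **Placebo is shown.** A reader might infer that only within-arm change is left, so that shared drift would pass for a drug effect. Placebo is summarised alongside, no within-arm test is planned, and a crude difference can be formed from the per-arm summaries. This stands, but that difference would be neither prespecified nor adjusted, and for PD it would be as treated.
- **The mechanism is not wholly untested.** A reader might infer that it is. Protocol 2.2 names atrophy beside SELs and rim lesions. Brain volume has an MMRM contrast, a sensitivity analysis excluding open-label data, and a place in the hierarchy. This stands.
- **A model does not by itself give a clean randomised estimate.** NfL, Chi3L1 and Ig sampling stops when IMP is discontinued (Protocol 1.3 footnote e, 7.1.1 and 8.6), and some participants cross over. MTR recovery and SEL T1 intensity exist only in participants with the relevant lesions after randomisation. Phase rim data come from 3T centres only, and lymphocyte data from up to 200 participants. This stands and shapes the fix.

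The as-treated reading is also not settled. SAP 3.1 presents open-label period summaries by original randomised group, which suggests that the section 2 rule may not have been meant for switchers. Section 3.7.2 should say so.

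**Conclusion.** The gap is real and small. As written, no prespecified estimate by randomised arm, with a CI, will exist for the four PD secondary endpoints or for SEL number, SEL volume and phase rim lesions. The PD grouping is open to a reading that mixes placebo switchers into tolebrutinib. Similar endpoints in the same SAP have modelled contrasts, and no reason for the difference is given.

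Nothing here touches the primary analysis, type I error or the tested secondary endpoints. The value of the change is a stated, baseline-adjusted contrast that would probably be informative for NfL and imprecise for lymphocyte subsets. That rests on the assumed SD and completeness, and on data after IMP discontinuation being missing at random.

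**What to change.** Before unblinding, amend three places in the SAP.

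- **Section 3.7.2.** For log NfL, log Chi3L1 and log Ig, report the tolebrutinib/placebo ratio of geometric means with 95% CI, by randomised arm. Use an MMRM with treatment, visit, treatment-by-visit, log baseline, baseline-by-visit, age group and region. Exclude samples taken after the start of open-label tolebrutinib, or show both versions. State that sampling stops at IMP discontinuation, so the estimate is largely on-treatment and assumes data missing at random. Treat a lymphocyte-subset contrast as optional.
- **Section 3.4.2.** Add a nominal contrast by randomised arm for SEL number (negative binomial), SEL volume (ANCOVA on log volume, adjusted for baseline T2 volume) and change in phase rim lesion count (3T subset). Report MTR recovery and SEL T1 intensity descriptively by arm, and say why they are not modelled.
- **Section 2.** Say whether the rule on receiving more than one intervention applies to open-label switchers.

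Prespecify one or two timepoints. Table 9 gives seven post-baseline timepoints, counting EOS, for NfL and Chi3L1 and six for Ig, so reporting all of them would multiply comparisons. Label every result nominal and outside the hierarchy.

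The cost is a few SAP paragraphs and some extra tables on data already scheduled for collection. The downside is several more nominal comparisons that are not multiplicity-controlled. If the sponsor prefers to stay descriptive, one sentence in 1.2.1 limiting the stated comparison to endpoints with a planned contrast would at least make the choice explicit.
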